5. TREATMENT ALLOCATION AND BLINDING

Treatment Allocation

Procedures for Randomization and Stratification

Central randomization will be implemented in this study. Subjects will be randomly assigned to 1 of 2 treatment groups based on a computer-generated randomization schedule prepared before the study by or under the supervision of the sponsor. The randomization will be balanced by using randomly permuted blocks and will be stratified on subjects' baseline C-peptide AUC (<0.66 pmol/mL, ≥0.66 pmol/mL) derived from the 4-hour MMTT conducted at screening. The interactive web response system (IWRS) will assign a unique treatment code, which will dictate

the treatment assignment and matching study agent kit for the subject. Members of the study site will have unique user and personal identification numbers to contact the IWRS and must provide relevant subject details to uniquely identify the subject.

Blinding

This will be a randomized, double-blind, placebo-controlled study. To maintain the study blind, the study agent container will have a multipart label containing the study name, study agent number, reference number, and other information on each part. The label will not identify the study agent in the container. However, if it is necessary for a subject's safety, the study blind may be broken, and the identity of the study agent ascertained. The study agent number will be entered in the case report form (CRF) when the study agent is administered. The study agents will be identical in appearance and will be packaged in identical containers.

The investigative sites will not be provided with randomization codes. The codes will be maintained within the IWRS, which has the functionality to allow the investigator to break the blind for an individual subject.

Data that may potentially unblind the treatment assignment (ie, study agent serum concentrations, anti-golimumab antibodies, and treatment allocation) will be handled with special care to ensure that the integrity of the blind is maintained and the potential for bias is minimized. This can include making special provisions, such as segregating the data in question from view by the investigators, clinical team, or others as appropriate until the time of DBL and unblinding.

Under normal circumstances, the blind should not be broken until all subjects have completed the study and the database is finalized. Otherwise, the blind will be broken only if specific emergency treatment/course of action would be dictated by knowing the treatment status of the subject. In such cases, the investigator may in an emergency determine the identity of the treatment by contacting the IWRS. It is recommended that the investigator contact the sponsor or its designee if possible, to discuss the particular situation, before breaking the blind. Telephone contact with the sponsor or its designee will be available 24 hours per day, 7 days per week. In the event the blind is broken, the sponsor must be informed as soon as possible. The date and reason for the unblinding must be documented by the IWRS, in the appropriate section of the CRF, and in the source document. The documentation received from the IWRS indicating the code break must be retained with the subject's source documents in a secure manner.

Subjects who have had their treatment assignment unblinded for a SAE will not continue to receive study agent but should continue to return for scheduled evaluations.

Summary level unblinded data will be made available to the sponsor at the Week 52 DBL (DBL 1). Subject level data will be unblinded to selected members of the sponsor's data management, programming, pharmacology, clinical and biostatistics teams for analysis and reporting, while the subjects are still being followed in the study. Identification of sponsor personnel who will have access to the unblinded subject level data will be documented prior to unblinding. The Study Responsible Physician will remain blinded throughout the double-blind

period to subject level treatment assignment and dosing regimen. Site investigators and personnel, and the subjects/caregivers will remain blinded until after the Week 104 DBL (DBL 2) has occurred. An exception to this rule will be made for those subjects who are meeting the responder criteria at Week 52 of the double-blind period. These will be unblinded to determine eligibility for re-starting active treatment during the open-label extension period.

Subject level data will be unblinded to Data Monitoring Committee (DMC) and Interim Analysis Committee (IAC). Please refer to Section 11.10 and Section 11.11 for details.

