The duration of study participation will be 108 weeks, including screening and post-randomization. Following screening, subjects must be randomized within 28 days. Following randomization there will be a 52-week treatment period with study agent followed by a 52-week off-therapy follow-up period.

Responders at Week 52 who are still in the follow-up period and who are determined to be in the active treatment group will have the option to restart active therapy while the non-responders will continue to follow the originally planned study design, ie, the off-therapy follow-up monitoring period.

There will be an open-label extension period of the study for responders. Responders are defined as subjects who have profile at Week 52 which includes:

1. C-peptide and Remission score* responders (C+R responders): either having an increase in C-peptide AUC versus baseline or having a stable C-peptide AUC, not decreasing more than 5% versus baseline and having a remission score ≤ 9 .
OR
2. C-peptide responders (C responders): either having an increase in C-peptide AUC versus baseline or having a stable C-peptide AUC, not decreasing more than 5% versus baseline but not meeting a remission score of ≤ 9 . Their remission score, however, must be < 12 .
OR
3. Remission score responders (R responders): having a remission score ≤ 9 but not meeting C-peptide response as defined above. However, their C-peptide AUC decline from baseline should be less than or equal to 30% compared to baseline.

*Insulin Dose Adjusted HbA1c: IDAA1c= A1C (percent) + [4 × insulin dose (units per kilogram per 24 h)].

This study will enroll male and female subjects 6 through 21 years of age who have been recently diagnosed with T1D and are able to be randomized within 100 days of diagnosis. A target of approximately 81 subjects will be randomly assigned in a 2:1 ratio to receive golimumab or placebo, administered SC for 52 weeks and monitored for an additional 52 weeks. Subjects will be randomized to receive active therapy (golimumab) or placebo and be stratified based on C-peptide AUC levels of < 0.66 pmol/mL or ≥ 0.66 pmol/mL from a 4-hour MMTT conducted at study screening. The protocol will give the option for study agent administration by the subject or caregiver outside of the study site, ie, self-administration, after proper training.

An independent Data Monitoring Committee will be commissioned to continually assess the safety of study subjects.

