2. OBJECTIVES, ENDPOINTS, AND HYPOTHESIS

2.1. Objectives and Endpoints

- Double-Blind Period

Objectives	Endpoints
Primary Objective and Endpoints	

 • To determine if golimumab can preserve β-cell function in children and young adults with newly diagnosed T1D. 	
 • The Mixed-meal Tolerance Test (MMTT) - stimulated 4-hour C-peptide area under the concentration-time curve (AUC) at Week 52.
Secondary Objectives and Endpoints: Efficacy	

 • To evaluate the impact of golimumab on measures of diabetes control in this subject population. • To evaluate the off-therapy durability of golimumab on measures of diabetes control in this subject population. 	
 • Change from baseline in insulin use in units per kilogram body weight per day over time. • Change from baseline in HbA1c over time. • Hypoglycemic event rates (defined as BG of ≤ 70, 55, and 35 mg/dL or clinical sequelae in the absence of a BG reading) through Week 52, after Week 52 through Week 104, and the entire study. • MMTT-stimulated 4-hour C-peptide AUC over time.

Objectives	Endpoints
Secondary Objective and Endpoints: Safety	

 To determine the safety and tolerability of golimumab in children and young adults with T1D. 	
 Proportion of participants with treatment-emergent AEs and severe AEs through Weeks 52 and 104. Proportion of participants with severe infections through Weeks 52 and 104. Proportion of participants with study agent injection site reactions through Week 52.
Secondary Objective and Endpoints: Pharmacokinetics (PK) and Immunogenicity	

 To evaluate the PK and immunogenicity of golimumab in this specific subject population with T1D. 	
 Summary of serum golimumab concentrations and the PK profile after induction and maintenance dosing. Incidence and titers of antibodies to golimumab.
Exploratory Objective and Endpoints: Immunologic and Metabolic	

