Per inclusion criteria, all randomized subjects will have a C-peptide level of ≥ 0.2 pmol/mL from a 4-hour MMTT at screening. Stratification will be employed based on subjects baseline MMTT-stimulated C-peptide AUC level as previous interventional studies in new-onset T1D suggest the response to immune therapies in new-onset T1D studies may be influenced, at least in part, by subject’s baseline endogenous β -cell function.^{31,55} To achieve balanced populations in the 2 treatment groups, eligible subjects will be randomized based on 2:1 ratio to receive active study agent or placebo within each stratum (< 0.66 pmol/mL or ≥ 0.66 pmol/mL). This stratification threshold of 0.66 pmol/mL was chosen based on simulations and calculations derived from existing data that this level is expected to be close to the median of the baseline MMTT-stimulated 4-hour C-peptide AUC of the study population.^{27,60}

Following database lock for the double-blind treatment period (Week 52), subjects who are still in the off-therapy follow-up period (Week 52 to 104 visits), who were on active drug during the double-blind period and who meet the response criteria will be offered the option to participate in the open-label extension period if eligibility criteria are met. Prior to initiating open-label screening assessments, subjects and parents/legal guardians will sign updated informed consent form (ICF)/assent forms.

Subjects who did not meet the response criteria at Week 52 will continue the off-therapy follow-up period.

Subjects who met the response criteria but either declined to participate in the open-label extension period, or were determined to be on placebo, will continue the off-therapy follow-up period as planned.

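### Section 5 breaks the site and subject blind for every Week 52 responder, including placebo responders who cannot enter the extension and stay in off-therapy follow-up

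*Protocol*

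**What the plan says.** Protocol Section 5 sets the general rule: "Site investigators and personnel, and the subjects/caregivers will remain blinded until after the Week 104 DBL (DBL 2) has occurred". It then departs from it: "An exception to this rule will be made for those subjects who are meeting the responder criteria at Week 52 of the double-blind period". The stated reason is eligibility: "These will be unblinded to determine eligibility for re-starting active treatment during the open-label extension period". The exception mentions neither treatment arm nor whether the subject is still in follow-up.

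The extension itself is narrower. In the Synopsis and Section 3.1, only responders "who are determined to be in the active treatment group will have the option to restart active therapy". Section 3.2.1 says that responders who decline, "or were determined to be on placebo, will continue the off-therapy follow-up period as planned".

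The same paragraph of Section 5 gives some sponsor personnel the codes at the Week 52 lock (DBL 1): "Subject level data will be unblinded to selected members of the sponsor" and its named functions, with access documented beforehand.

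Section 2.1 makes the follow-up year serve a secondary objective: "To evaluate the off-therapy durability of golimumab on measures of diabetes control in this subject population". Its endpoints are insulin use, HbA1c, hypoglycemia rates (including Week 52 to 104) and C-peptide AUC over time. The SAP Introduction limits that document to the Week 52 lock, so neither document says how partly unblinded follow-up data would be analyzed.

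**The concern.** Section 3.2.1 justifies blinding partly as protection against bias in data collection. Several follow-up measures depend on what subjects and their care teams do. Section 8.1 leaves insulin adjustment to the investigator or treating physician, and Section 9.8 has subjects record their own insulin use and suspected hypoglycemia. Someone told that they were on placebo, or that they responded to golimumab, may dose, test or report differently.

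The unblinded group is also selected: it consists of subjects with good Week 52 outcomes, while non-responders stay blinded. Knowledge of treatment would thus enter the durability comparison through one end of each arm's outcome distribution. For placebo responders the exposure gains nothing, since they cannot be offered re-treatment.

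**Working it through.** **1. Who is unblinded, and to whom.** The sentence in Section 5 is an exception to the blind of sites, subjects and caregivers. It cannot sensibly mean disclosure to sponsor staff only, because that paragraph already gives them access at DBL 1. Its only condition is response, so it covers placebo responders. It also covers responders whom Section 4.2.2 already bars, such as those who stopped study agent before Week 52 or have completed Week 104. Both facts can be known without the code.

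**2. What eligibility needs.** Arm must be known to decide who may restart. Section 3.2.1 places the offer after DBL 1, when the designated sponsor staff have both the codes and the Week 52 data. Footnote p of the open-label Time and Events Schedule already assumes that sites are notified of responders. Arm can therefore be checked before notification, without telling a placebo subject's site.

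**3. The plan's own design figure.** Section 11.2 states 90% power. On log(AUC+1):
- difference = ln(1.635) − ln(1.385) = 0.1659
- SE = 0.215 × √(1/27 + 1/54) = 0.0507
- power = 0.906 (normal approximation) or 0.899 (noncentral t, 79 df)

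The figure reproduces. It concerns Week 52 only, and the unblinding comes after that lock, so it is not affected.

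**4. Share of visits still pending at unblinding.** Section 3.1 gives enrollment over E = 12 to 18 months and places DBL 1 after all subjects complete Week 52. Assume uniform enrollment and a lag of L = 0 to 4 months from the last Week 52 visit to unblinding. A subject enrolled at month t has been followed for 12 + L + (E − t) months. Hence:
- Week 104 pending = min(1, (12 − L)/E)
- Week 78 pending = (6 − L)/E

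| E | L | Week 78 pending | Week 104 pending |
|---|---|---|---|
| 12 | 0 | 50% | 100% |
| 12 | 2 | 33% | 83% |
| 12 | 4 | 17% | 67% |
| 18 | 0 | 33% | 67% |
| 18 | 2 | 22% | 56% |
| 18 | 4 | 11% | 44% |

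**5. Placebo subjects affected.** The documents give no responder rate. Assume 10-30% of 27, or 2.7 to 8.1 subjects, with response unrelated to enrollment date.
- Week 104 visit made unblinded: 2.7 × 0.444 = 1.2, up to 8.1 × 1.0 = 8.1, so about 1 to 8.
- Week 78 visit made unblinded: 2.7 × 0.111 = 0.3, up to 8.1 × 0.50 = 4.1, so about 0 to 4.

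Hypoglycemia is recorded continuously. Part of the Week 52 to 104 rate is therefore exposed even in a subject whose Week 78 visit came first.

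**The case against.** **The unblinding has a stated purpose.** A reader might infer that it serves none. The documents do not support that: Section 5 gives eligibility as the reason, and arm must be known to decide it. What stands is narrower: the purpose does not require sites to learn the arm of subjects who cannot be offered treatment.

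**Most follow-up data are not lost.** A reader might infer that the Week 78 and Week 104 data as a whole become open-label. They do not. Non-responders stay blinded, and many Week 78 visits and some Week 104 visits would already be done. C-peptide AUC is a laboratory measure, HbA1c is assayed centrally, and glycemic targets do not differ by arm. The primary endpoint and all three major secondary endpoints in Section 9.2.2 are at or through Week 52. That section lists the later measures as other endpoints, although Section 2.1 makes durability a secondary objective. These points limit the concern's weight but do not remove it for insulin use and hypoglycemia reporting.

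**The remedy leaks.** Sites hold HbA1c and insulin data, and the protocol prints the remission-score formula and cut-offs. A site that recognizes a responder and receives no notification could infer placebo. This stands in part. All three responder definitions in Section 3.1 also need the C-peptide AUC change, so HbA1c and insulin alone do not settle status. The documents do not say whether sites receive C-peptide results, and Section 5 does not list them among data that could unblind.

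**The remedy is one-sided.** Only golimumab subjects would then be unblinded at site level, including decliners who remain in follow-up. It also does nothing about golimumab responders who restart treatment and so leave the off-therapy comparison. Both points are true. They are limits of the change, not reasons to disclose placebo assignments.

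**Conclusion.** The point holds in a limited form. As written, Section 5 discloses assignment more widely than eligibility needs, and does so in a response-selected subset whose behavior-dependent follow-up data serve a secondary objective. The exposure is mainly at Week 104, for some subjects at Week 78, and in the hypoglycemia record after unblinding.

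About 1 to 8 of 27 placebo subjects would reach Week 104 unblinded. This rests on an assumed 10-30% placebo responder rate, uniform enrollment over 12-18 months and a 0-4 month lag. The top of the range needs the highest rate, the shortest enrollment and no lag. A reader might take 30% of the control arm (8 of 27) as the expected effect. The documents do not support that, because they give no responder rate and it ignores visits already completed. The direction and size of any bias cannot be derived from the documents. The Week 52 conclusions do not depend on this point.

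**What to change.** Reword the Section 5 exception. After DBL 1, the documented unblinded sponsor staff identify subjects who were on golimumab, met the responder criteria and have not completed Week 104. Sites are notified of these subjects only. All others, including placebo responders, stay blinded until DBL 2. Responder classification is not reported to sites, nor is post-baseline C-peptide if sites would otherwise receive it; the sponsor should confirm whether they do.

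In the Week 104 analysis plan, flag data collected after a subject's unblinding, and present insulin use, HbA1c and hypoglycemia with and without those data.

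The cost is amendment wording, a central check by staff who already hold the codes, a narrower version of the existing notification step, and a little extra analysis. If sites now receive C-peptide results, withholding them is a further operational change. The downsides remain: golimumab responders who decline are still unblinded, site-level unblinding then occurs only in the golimumab arm, and sites may partly infer response from HbA1c and insulin data.

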6. DOSAGE AND ADMINISTRATION

6.1. Dosage

All study agent (golimumab or placebo) will be administered SC using a sponsor-supplied, single-use administration device. This will be either the commercially available prefilled syringe with a needle guard (the PFS-Ultrasafe [PFS-U]), designed to deliver a single, fixed dose of 50 mg, or the investigational VarioJect injection device (“VarioJect”) which delivers a single, variable dose of 10 to 45 mg in 5 mg increments. Identical devices containing placebo will be used to deliver a volume equivalent to that of active treatment for subjects randomized to the placebo arm.

Body surface area will be calculated at Week 0 for the induction and maintenance dose of golimumab (and will be adjusted as needed) based on weight cut-off according to [Table 1](#). Detailed charts using height and weight for induction and maintenance doses according to weight cut-off are presented in [Attachment 2-A](#) and [2-B](#), respectively. Body surface area will be calculated using the Mosteller equation: $BSA (m^2) = ([\text{height (cm)} \times \text{weight (kg)}] / 3600)^{1/2}$. The dosage form (PFS-U or VarioJect) and volumes required for administration are presented in [Attachment 2-C](#). For certain induction doses, 2 injections may be required for administration of 1 induction dose.

Body weight*	Week 0 and 2	Week 4 through Week 52 (Double-Blind) Period	Week 0 through Week 50 (Open-Label Extension) Period
<45 kg	60 mg/m ²	30 mg/m ² q2w	30 mg/m ² q2w
≥45 kg	100 mg	50 mg q2w	50 mg q2w
Number of injections/dose	1 or 2**	1**	1**

*Body weight to be evaluated approximately every 3 months with dose adjustment if necessary (below and see [Time and Events](#) Table).

**Refer to [Attachment 2](#)

During the 52-week dosing period, subjects may experience changes in their weight and/or height necessitating a change in the dose of the study agent. There will be 4 opportunities to calculate the study agent dose during the 52-week dosing period. Study agent dose for the first 12 weeks will be based on height and weight obtained at the Week 0 visit. At the Week 12 visit, height and weight will be obtained and the dose for the next 14 weeks (until the Week 26 visit)

will be calculated. Similarly, at the Week 26 and 38 visits, the dose for the subsequent 12 and 14-week intervals, respectively, will be calculated (see [Time and Events Schedule](#)).

The same procedure will be applied for the responders during the open-label extension period. Study agent dose will be calculated at the OL Week 0, 12, 28, 44, and 50 visits. The last dose of study agent is to be administered at Week 50. Detailed charts using height and weight for open-label extension period according to weight cut-off is presented in Attachment 2-B.

Responders being restarted on active drug will not undergo an induction regimen but will immediately be started on the maintenance dose. A new induction dose may entail an increased risk for immunogenicity and/or hypersensitivity reactions and there is no clear rationale for reaching steady state as quickly as possible given the longer delay after diagnosis of T1D.

Details on dose preparation and administration can be found in the Study Site Investigational Product and Procedures Manual (SIPPM).

For the most comprehensive information regarding the VarioJect, refer to the current version of the VarioJect IB.

6.2. Dose Administration

Study agent dosing will be administered using the PFS-U or VarioJect. It will be injected subcutaneously by trained study-site staff and for some dosings, subjects/caregivers will be given the option of "self-administration" after appropriate training (described below). For purposes of this study, the term "self-administration" is defined as study agent administered either by subject or caregiver and can occur at home and/or at study sites. In cases where subjects/caregivers do not want or are unable to participate in self-administration of study agent, subjects will receive all doses of study agent at study sites.

For responders in the open-label extension period, study agent administration will be performed by site personnel at all site visits. In-between visit doses will be administered either by the subject or by the caregiver. In cases where subjects/caregivers do not want or are unable to participate in self-administration of study agent, subjects will receive all doses of study agent at study sites.

Study staff and those subjects/caregivers who will participate in self-administration will receive training on study agent administration at the investigative site under the supervision of a trained health care professional, which must be documented. This will include education regarding instructions for use (IFU), proper handling and storage of devices, guidance on study agent injection, and proper handling and accounting for used devices. Required storage conditions and expiration date are indicated on the label.

Injection sites include the front of thighs (which is recommended), the lower abdomen (avoiding the 2-inch area around the navel), or the back of the upper arms. Different sites should be used for consecutive injections. Sites that are tender for any reason should be avoided. Study agent and insulin injections should be given at different anatomic sites.

Study agent dosing should be held during the course of a febrile episode and other conditions as detailed Section 10.2. If the febrile episode is mild and transient and the subject does not meet any criteria in Section 10.2, that dose may still be administered as long as it is in the current dosing window (See Section 7.1) otherwise dosing should resume with the next planned dose. Refer to Section 10.2 for dose holding and dosing resumption for other conditions. If subjects/caregivers have a question about the subject status and their ability to be dosed, they are to consult with the study-site investigational team. If subjects/caregivers have a question about the subject status and their ability to be dosed, they are to consult with the study-site investigational team.

Administration of the first 3 doses will occur during study visits (Week 0, 2, and 4). For subjects/caregivers who will be participating in self-administration, training will take place at these visits. It is possible that the device required for induction doses differs from the device required for maintenance doses. Training should be provided on the device intended for maintenance dosing. Prior to allowing at home self-administration, at least 1 successful injection by the subject/caregiver using the device to be used for at home self-administration, must be witnessed by study staff. At the Week 8, 12, 18, 26, 38, and 52 study visits of the double-blind period and Week 12, 20, 28, 36, 44, and 50 study visits of the open-label extension period where study agent will be administered, either subjects/caregivers or study staff may administer the injection.

Following dosing, subjects are to be monitored for at least 30 minutes as detailed in Section 9.1.3 and Section 9.1.5. All data regarding study agent administration including date, time, and anatomic location of injection, study agent dosing device and if there are AEs, reactions or device complications will be recorded. During self-administration, subjects/caregivers are to contact the study-site team in the event of problems or complication including but not limited to signs of immediate or delayed local or systemic reaction (Section 9.9).

At any time, if subjects/caregivers are uncertain about how to administer the study agent or has questions regarding self-administration, the sponsor recommends a review of the IFU with the study staff along with practice injections with a training device if necessary. If at any time during one of the 3 opportunities for dose adjustment, there is a change in the device required for dosing, the subject/caregiver must return to the study site for training and the subject/caregiver using the device must be witnessed by study staff self-administering a successful injection prior to performing at home self-administration.

For subjects/caregivers unwilling or unable to self-administer the study agent outside of the study site, subsequent doses will be administered at the study site by qualified personnel on the appropriate dosing schedule per the [Time and Events Schedule](#). During the dosing period these subjects/caregivers can be trained for self-administration of subsequent dosing per the above guidelines.

